9.4 Baseline data

All patients will have a full medical history taken and a clinical examination as part of the admission process. The following routine tests are to be recorded:

- a) Weight
- b) Sex
- c) Age
- d) Liver disease and indication for transplant
- e) Full blood count (including platelets and differential white cell count)
- f) INR
- g) Biochemical series (including creatinine, sodium, bilirubin, alkaline phosphatase, AST/ALT) to allow calculation of UKELD, MELD and MELDNa scores

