5.6 Study endpoints

5.6.1 *Primary endpoint*

- Post reperfusion intra-operative blood loss
- Feasibility of adding TPA and FFP to livers undergoing normothermic perfusion before transplantation

5.6.2 *Secondary endpoint*

- Return to theatre in first 24 hours for bleeding
- Total and post reperfusion intra-operative blood transfusion
- Liver utilisation: proportion of liver perfusions resulting in a transplant
- Incidence of symptomatic anastomotic and non-anastomotic strictures at 6 months post-transplant
- Incidence of any anastomotic or non-anastomotic stricture excluding those related to hepatic artery thrombosis
- Incidence of “clinically relevant” non-anastomotic strictures, using the van Rijn definition¹¹
- Incidence of post reperfusion syndrome: 30% fall in mean BP lasting at least a minute in the first 5 minutes post reperfusion or the need for adrenaline or doubling of noradrenaline to support the circulation.
- Early allograft function (Olthoff criteria¹² and MEAF score¹³)
- Incidence of hepatic artery thrombosis in the first 6 months
- Incidence of acute kidney injury (RIFLE criteria)
- D-dimer release into perfusate compared to controls

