10.4.4 Acute kidney injury

Acute kidney injury will be defined by the RIFLE criteria as a creatinine in the first 7 days post-transplant which has risen more than two-fold higher than the pre-transplant value, or the need for haemofiltration or dialysis. The peak to baseline values will also be compared.

The ratio of peak (d1-7) over baseline creatinine will also be recorded and compared with historical comparators; the absolute percentage where the ratio is ≥ 2.0 will also be compared.

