10.5 Statistical methods to be employed

Descriptive data will be presented as median, interquartile range or range (continuous variables) or number, percentage (categorical variables) and compared using the Kruskal-Wallis test (continuous variables) and Fisher's exact test (categorical variables). Survival will be compared with log rank analysis.

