10.6 Analysis plan

Transplant recipients in the pilot study will be compared with twice the number of recipients of DCD livers that were machine perfused in the recipient centres in the previous 2 years. They will be matched for agonal phase duration, cold ischaemia time and UK donor liver index ¹⁶.

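### The historical DCD comparison is matched on donor and preservation factors only and tested without adjustment, so differences in recipient severity can bias the bleeding and early-function results

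*Protocol*

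**What the plan says.** Section 10.6 sets up a non-randomised comparison. Pilot recipients are to be "compared with twice the number of recipients of DCD livers that were machine perfused in the recipient centres in the previous 2 years". On how these are chosen it says: "They will be matched for agonal phase duration, cold ischaemia time and UK donor liver index". The list contains no recipient characteristic.

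Section 10.5 gives the tests. Data are to be "compared using the Kruskal-Wallis test (continuous variables) and Fisher's exact test (categorical variables"), with log rank for survival. All are unadjusted.

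Section 9.4 lists recipient weight, full blood count with platelets, INR, creatinine, sodium and bilirubin, the biochemistry being taken "to allow calculation of UKELD, MELD and MELDNa scores". No visible section uses these scores, INR or platelets to match, stratify or adjust.

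The first primary endpoint in section 5.6.1 is "Post reperfusion intra-operative blood loss". Transfusion and early allograft function are secondary endpoints. Section 10.4.4 sends one kidney outcome explicitly to the historical group: "The ratio of peak (d1-7) over baseline creatinine will also be recorded and compared with historical comparators". For bleeding and early function the historical comparison follows from the general wording of section 10.6.

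There is also a concurrent comparator. Sections 2.9 and 7 randomise one transplanted liver in six to FFP without TPA.

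**The concern.** Matching on donor and preservation factors makes the livers comparable. It does nothing for the patients who receive them. Bleeding after reperfusion can be expected to depend on the recipient's coagulation and severity of liver disease, and INR and bilirubin, which enter the definition of early dysfunction in section 10.4.3, on the recipient's starting state. Randomisation does not balance these against a historical group.

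The protocol's own rules make a difference in severity plausible. Section 6.2 excludes recipients who cannot consent. Section 9.3 records no research data for unconscious or encephalopathic urgent recipients unless they consent afterwards. No such restriction is stated for the historical recipients, who also come from an earlier period. If the trial recipients are less sick, they bleed less for that reason, and a real excess due to TPA could be hidden. In a pilot whose primary objective is safety, that is the more worrying direction.

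**Working it through.** **The plan's own figures.** The protocol states no power, effect size, alpha or SD for blood loss. Its only derived figures are the livers to be perfused: 30/(1 − 1/3) = 45 DCD and 30/(1 − 0.15) = 35.3 DBD. They agree with the stated 45 and around 35 and do not bear on this point.

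**Inputs from the protocol.**
- DCD transplants: 30 (section 5.4).
- FFP-only: one in six (section 7), so 30/6 = 5 controls and 25 on TPA.
- Historical recipients: 2 × 30 = 60 (section 10.6).
- Expected kidney injury in DCD recipients: 50% (section 11.3).

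**Inputs assumed.**
- Two-sided 5% test.
- Blood loss roughly normal with SD 1 on a suitable scale, such as the log.
- Correlation r of recipient severity with blood loss: 0.3 or 0.5.
- Difference d in mean severity between the groups: 0.25 or 0.5 SD.
- True TPA excess, where there is one: 0.5 SD.

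**Method.** The spurious shift in blood loss is r × d. The standard error of the difference is √(1/25 + 1/60) = 0.238. The noncentrality is shift/0.238, referred to a t distribution with 83 degrees of freedom. In the masking direction the visible effect is 0.5 − r × d. With no imbalance the noncentrality for 0.5 SD is 0.5/0.238 = 2.10, giving power of 55%.

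| d | r | Shift r × d | False-positive rate, no TPA effect | Power for a true 0.5 SD excess, masked |
|---|---|---|---|---|
| 0 | – | 0 | 5% | 55% |
| 0.25 | 0.3 | 0.075 | 6.1% | 42% |
| 0.25 | 0.5 | 0.125 | 8.1% | 34% |
| 0.5 | 0.3 | 0.150 | 9.5% | 31% |
| 0.5 | 0.5 | 0.250 | 18.0% | 18% |

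A simulation of the Kruskal-Wallis test that section 10.5 names (40,000 runs per case, normal data) gives nearly the same: false-positive rates of 6.1%, 7.9%, 9.4% and 17.7%, and power falling from 53% to 40%, 33%, 29% and 18%.

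If all 30 DCD pilot recipients are compared with 60, false-positive rates run from 6% to 20%. At d = 0.5, power falls from 60% to 34% (r = 0.3) or 20% (r = 0.5).

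**Gain in precision if severity is balanced.** Adjustment turns the standardised effect into 0.5/√(1 − r²): 0.524 at r = 0.3 and 0.577 at r = 0.5. At 25 v 60, power goes from 55% to 59% and 67%.

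**Kidney injury.** From 50% in both groups, Fisher's exact test at 25 v 60 rejects 3.2% of the time. An assumed spurious difference of 3, 6 or 9 percentage points moves that to 3.7%, 5.4% or 8.2%.

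**Randomised comparison.** With 25 v 5 the standard error is √(1/25 + 1/5) = 0.490, about twice the 0.238 of the historical comparison.

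**The case against.** The strongest reply is that covariates and model form usually belong in the SAP, which is not at hand, and that section 10.5 does not forbid adjustment. A later SAP could indeed add it. But section 10.6 is not silent: it names the matching variables, and they leave out the recipient. Followed as written, the plan leaves the gap open.

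Several stronger readings are tempting, and the protocol does not support them.

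- A reader might infer that the baseline recipient data are not used at all. Section 10.4.4 does use baseline creatinine: kidney injury is a creatinine that has "risen more than two-fold higher than the pre-transplant value, or the need for haemofiltration or dialysis". Indexing to the recipient's own value partly handles baseline level for that endpoint. It does not balance overall severity, and the dialysis limb states no exclusion for dialysis before transplant.
- A reader might infer that every conclusion about TPA rests on the historical group. The FFP-only controls give a comparison that avoids this bias by design, but with about five DCD controls it is too imprecise to replace the historical one.
- A reader might infer a false bleeding signal. No direction is established.
- A reader might blame changes of recipient under section 9.2. That section calls them rare, and where it refers to urgency it mentions only a recipient of greater urgency.

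It is also fair that this is an unpowered pilot, so the gain in power is secondary. The case for adjustment rests on bias.

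**Conclusion.** The concern holds for recipient bleeding endpoints and early function in the historical DCD comparison. Section 10.6 describes no historical group for DBD livers, so the point does not extend to them. For kidney injury it holds weakly.

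On the assumed values, the distortion of the false-positive rate is modest at a 0.25 SD imbalance (6–8%) and material at 0.5 SD (about 10–18%). At 0.5 SD the loss of power in the masking direction is large, from about 55% to 18–31%. These figures illustrate what an imbalance of that size would do. They do not show that one exists, because the protocol gives no severity distribution, no correlation and no spread for blood loss. The point should be corrected: it bears on the primary safety question, and the pilot recipients' data are already being collected.

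**What to change.** In section 10.6, for the historical comparison, add a regression on log blood loss, and one on the MEAF score, containing the three matching variables plus one recipient severity score (MELD or UKELD). Add platelets for the bleeding endpoints. Use one score only, and do not add INR separately beside MELD, which already contains it. Report the adjusted difference with a 95% confidence interval beside the unadjusted result. Extract the same routine pre-transplant bloods for the historical recipients.

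The cost is some extra extraction from historical records, which have to be consulted for outcomes in any case, and a few degrees of freedom. Sample size, treatment and visits do not change. Adjustment removes only the measured part of the imbalance, so the comparison should still be reported as non-randomised.

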9.5 Study assessments

9.5.1 Perfusate and biopsy samples

	Liver biopsy*	Perfusate sample (10ml)	Recipient blood sample
Liver benchwork	x		
Pre-perfusion		x	
30 min		x	
60 mins		x	
90 mins		x	
120 mins		x	
180 mins		x	
240 mins		x	
Immediately before removal from machine	x	x	x
60 – 120 mins after reperfusion in recipient (at close)	x		x

* Liver biopsies will involve dividing the routine clinical biopsies into two, sending one half for histopathology and the other will be stored in RNALater for RNA analysis.

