2.9 Trial summary

Livers from donors donating after circulatory arrest (DCD donors) are associated with a high incidence of bile duct strictures after transplantation. This remains the case for liver subject to *ex situ* normothermic perfusion (NESLiP) prior to transplantation, with a rate of around 20% for anastomotic and non-anastomotic strictures. Livers from brain dead donors have a lower incidence of strictures after NESLiP at around is 8%, but they are equally disabling. Recent work in Cambridge has shown that DCD livers during NESLiP develop infarcts in the stromal walls of bile ducts in association with fibrin plugs in the peri-biliary blood supply, suggesting that these fibrin plugs may be the cause of the stromal infarcts, and by extrapolation the bile duct strictures. Subsequent work has shown that by using a similar thrombolytic protocol with tissue plasminogen activator (TPA, alteplase) to that used for clearing clots from the coronary circulation in patients having heart attacks results in no visible fibrin plugs and no bile duct necrosis.

In this study livers will undergo NESLiP and receive an infusion of TPA using a standard thrombolytic regimen for the first 60 minutes of perfusion, with a minimum perfusion time of 2 hours. Alteplase has a half-life of 5 minutes *in vivo* and a 1 hour perfusion will mean there will be at least 60 minutes between the end of the TPA infusion and removing the liver from the machine. Not all DCD donor livers will be viable on testing during NESLiP, but experience suggests that two thirds will meet the viability criteria and be transplanted. It is unlikely that there will be any active TPA in the circuit at the point of removal from the machine. Recipients will then undergo standard follow up with no further research intervention.

This study is a pilot study of 30 DCD and 30 DBD transplants to assess the safety of thrombolysis during *ex situ* perfusion, and to give an idea of its effects on the subsequent outcome of the implanted liver with particular reference to early function and bile duct strictures. The results will be compared with recipients randomised to receive FFP and no TPA. If the study suggests that the intervention is safe and efficacious the protocol will be used in a larger scale multicentre study.

3 Study Flow Chart

Donor liver placed on OrganOx *metra* machine

[figure not shown]

Figure 1: Flow chart for NESLiP assessment of donor livers

4 Background

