4.3 Investigational treatment

Alteplase (Actilyse, Boehringer Ingelheim, Germany) is a tissue plasminogen activator used routinely for the treatment of thrombotic occlusive events. *In vivo* it relies on the presence of plasminogen in clots and in the circulation which it breaks down to form plasmin, which is the active lytic component. Alteplase has a very short half-life *in vivo* (5 minutes according to the Summary of Product Characteristics, SmPC ⁶).

In the *ex situ* circuit there is no plasminogen circulating, although the liver will make some as time progresses; instead a plasminogen source is required and is readily available in the form of fresh frozen plasma (FFP) which has previously been shown to be effective as a perfusate component in NESLiP ⁷ as well as being a good source of plasminogen ⁸.

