4.6 Risks and benefits

The main risk of thrombolytic therapy is bleeding, but since this treatment will take place *ex situ*, and there will be a 60 minute washout period, there is likely to be little TPA left circulating. The plasma half-life of TPA *in vivo* is 4 to 5 minutes⁶. When the liver is removed from the perfusion machine it is flushed with 2 to 3 litres of preservation solution before being implanted, washing away any last traces of perfusate.

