5.8.3 Trial

The trial will end if:

- 30 DBD and 30 DCD livers have been transplanted
- Evidence of residual thrombolytic activity in the livers post transplant. However, it is common in DCD liver transplantation for the patient to become coagulopathic post implant with evidence of fibrinolysis
- ≥ 5 cases of anastomotic or non-anastomotic strictures within six months of transplant

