5.9.3 Perfusate samples

Perfusate samples will be taken before perfusion begins, at 30, 60, 90, 120, 180 and 240 minutes. 10mls will be taken and spun down and the cell free perfusate frozen for later analysis including assays of fibrin breakdown and markers of reperfusion injury.

6 Eligibility

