11.6.3.2 Follow-up reports of SUSARs

In case of incomplete information at the time of initial reporting, all the appropriate information for an adequate analysis of causality should be actively sought from the reporter or other available sources. The sponsor should report further relevant information after receipt as follow-up reports.

In certain cases, it may be appropriate to conduct follow-up of the long-term outcome of a particular reaction.

12 Data handling and record keeping

Data will be collated on a password controlled study database held on an encrypted partition of computer hard disc, or trust or university server.

13 Direct access to source data / documents

The investigators will permit trial related monitoring, audits, REC review, regulatory inspections.

14 Publications policy

Authorship will follow the guidelines of the International Committee of Medical Journal Editors (ICJME)¹ based on satisfying the following 4 criteria

- Substantial contributions to the conception or design of the work; or the acquisition, analysis, or interpretation of data for the work;
- Drafting the work or revising it critically for important intellectual content;
- Final approval of the version to be published;
- Agreement to be accountable for all aspects of the work in ensuring that questions related to the accuracy or integrity of any part of the work are appropriately investigated and resolved.

15 Finance

Since the intervention is to be in patients already having a DCD liver which is to undergo *ex situ* perfusion, the only study related expense is the provision of alteplase and fresh frozen plasma. This cost will be borne out of local funds at each participating hospital.

Subsequent analyses on biopsies and perfusate will be funded from future grants.

16 Ethical considerations

The investigators do not envisage any unusual ethical issues.

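### The trial-ending criterion on residual thrombolytic activity has no scheduled measurement that can separate carried-over TPA from usual post-transplant fibrinolysis

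*Protocol*

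**What the plan says.** - **Criterion.** Protocol section 5.8.3 lists "Evidence of residual thrombolytic activity in the livers post transplant" among the reasons to end the trial. It names no assay, threshold, time point or number of cases. Its next sentence warns that coagulopathy with fibrinolysis is frequent after DCD implantation in any case.
- **Recipient samples.** The table in section 9.5.1 has two recipient blood samples: one "Immediately before removal from machine" and one at "60 – 120 mins after reperfusion in recipient (at close"). No test is named for either.
- **Perfusate.** Section 5.9.3 says "Perfusate samples will be taken before perfusion begins, at 30, 60, 90, 120, 180 and 240 minutes". The cell-free fraction is frozen; the assays given as examples are fibrin breakdown and reperfusion injury. The table in 9.5.1 adds a perfusate sample just before removal, which 5.9.3 does not list.
- **Timing and funding of assays.** Section 4.7 plans perfusate D-dimer between groups, and sections 2.7.6 and 8.2 report that 10 mg data have already led to Group C being dropped. Section 15 adds: "Subsequent analyses on biopsies and perfusate will be funded from future grants".
- **Washout assumption.** Section 2.9 states: "It is unlikely that there will be any active TPA in the circuit at the point of removal from the machine". Section 4.3 gives the in vivo half-life as "5 minutes according to the Summary of Product Characteristics, SmPC"; section 4.6 says it "is 4 to 5 minutes" and relies on a 60-minute washout followed by a flush of 2 to 3 litres.

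**The concern.** A rule that can end a trial needs a measurement that responds to the thing it guards against. Here that is alteplase carried into the recipient in the graft. The rule is worded in terms of activity, but no scheduled test measures activity, and the sign most likely to be seen, fibrinolysis, is one the protocol itself expects without the drug.

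Excess bleeding in recipients is one of the two primary questions (section 4.9.1). If it occurs, the investigators would have to decide whether the criterion is met without data that separate drug carry-over from ordinary DCD coagulopathy. If it does not occur, the trial would still finish without having tested its claim that no active TPA remains at removal, a claim a larger trial would inherit.

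**Working it through.** **1. Reproduce the protocol's washout.** Minimum perfusion of 2 hours minus a 1-hour infusion (section 2.9): 120 − 60 = 60 min, as stated.

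**2. Place the recipient sample in half-lives.** Assuming first-order decay, half-lives elapsed = t / t½ and fraction remaining = 0.5^(t / t½), with t = 60 and 120 min after reperfusion. The documents give only an in vivo half-life, none for the ex situ circuit, so longer values are shown as assumptions.

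| t½ (min) | Source | Half-lives at 60 / 120 min | Left at 60 min | Left at 120 min |
|---|---|---|---|---|
| 4 | section 4.6 | 15 / 30 | 0.003% | 0.00000009% |
| 5 | sections 4.3, 4.6 | 12 / 24 | 0.024% | 0.000006% |
| 10 | assumption | 6 / 12 | 1.6% | 0.024% |
| 20 | assumption | 3 / 6 | 12.5% | 1.6% |
| 30 | assumption | 2 / 4 | 25% | 6.3% |

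On the stated half-life, a negative sample at close says almost nothing about activity at reperfusion.

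**3. Apply the same half-life to the washout.** For a 2 mg bolus and 8 mg over 60 min, with k = ln 2 / t½, the amount at the end of infusion is 2·e^(−60k) + (8/60)/k · (1 − e^(−60k)). Multiplying by 0.5^(60 / t½) gives the amount at removal, before the flush.

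- t½ = 5 min: 0.96 mg at the end of infusion, 0.96 × 0.000244 = 0.00023 mg at removal.
- t½ = 20 min (assumption): 3.62 mg, then 3.62 × 0.125 = 0.45 mg.
- t½ = 30 min (assumption): 4.83 mg, then 4.83 × 0.25 = 1.21 mg.

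Whether carry-over matters therefore depends on clearance in the circuit, which the protocol does not state. The pre-removal perfusate is the scheduled sample that addresses it directly.

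**4. Set each scheduled measure against the criterion.**

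- Recipient blood at close: no assay named; timing as in step 2.
- Biopsy after reperfusion (sections 5.9.1, 9.5.1): H&E and MSB histology and RNA, none of which measures thrombolytic activity.
- INR and platelets, days 1 to 10 (section 9.5.3): later still and not specific to alteplase.
- Perfusate D-dimer (section 4.7): available during the trial, but it marks fibrin already broken down and is used to judge efficacy.
- Blood loss, transfusion and return to theatre (section 5.6): consequences of bleeding, not its cause.

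**5. Check Group E.** Section 4.7 gives a 2-hour infusion. Against the 2-hour minimum perfusion in section 2.9, the guaranteed washout is 120 − 120 = 0 min, not the 60 min in sections 2.9 and 4.6. The table in section 8.2 shows Group E as a 10 mg bolus with 0 mg infused. These statements disagree.

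**The case against.** The strongest reply is that the half-life argument cuts both ways. If 4 to 5 minutes holds throughout, the washout alone spans 12 to 15 half-lives and the flush follows, so a blood sample drawn minutes after reperfusion would also find almost nothing. If clearance is slower, and stays slower in the recipient, the existing sample keeps some sensitivity (12.5% left at 60 min for a 20-minute half-life). This stands: sample timing is not the main defect, and an extra early blood tube is a preference.

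A reader might also infer that the criterion cannot be evaluated at all. The documents do not support that: it is not confined to alteplase concentration in blood, a positive late sample would still be evidence, and bleeding outcomes are collected.

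Nor do they support reading section 15 as meaning that no perfusate result will exist during the trial. D-dimer is planned between groups, and results have already changed the design. The list of assays in 5.9.3 is not exhaustive, and the omission of the pre-removal sample there is clerical, since 9.5.1 schedules it.

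Finally, safety does not rest on this criterion alone: there is a primary blood-loss endpoint, FFP-only controls and case reviews between sites (section 10.7). These can show excess bleeding. They cannot show whether carried-over TPA caused it.

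**Conclusion.** The point holds in limited form. Section 5.8.3 sets a trial-level safety stop for which no test is assigned, and its own qualifier removes the specificity of the most likely sign. Followed exactly, the plan cannot reliably separate carried-over TPA from usual fibrinolysis, and the assumption of no active TPA at removal goes untested.

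The size is given by the protocol's half-life: 12 to 24 half-lives at 5 minutes (up to 30 at 4 minutes), with 0.024% or less remaining when the at-close sample is drawn. This assumes first-order decay and that the in vivo figure applies after reperfusion. With a longer half-life the sample would be more informative, but the criterion would still have no named measurement.

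The Group E discrepancy is separate and does not depend on these assumptions.

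**What to change.** 1. Assay two samples already in section 9.5.1 for TPA activity, in TPA and FFP-only livers alike: the perfusate taken just before removal, and the recipient blood at close. Run them in the same between-group batches as D-dimer.
2. State in section 5.8.3 that the criterion is judged on that measurement, and that results must be available before the next group opens. Say that a negative at-close result does not exclude activity at reperfusion.
3. Treat the comparison with controls as descriptive. With one liver in six on FFP only (section 7), a group of six has one control, and 60 transplants would have about 60 / 6 = 10.
4. Add the pre-removal perfusate sample to the list in section 5.9.3 so that it matches 9.5.1.
5. Reconcile the Group E infusion in section 4.7, its row in section 8.2, and the minimum perfusion and washout in sections 2.9 and 4.6. Which of these is right is for the investigators to settle.

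The cost is protocol wording and a modest assay expense brought forward from the future grants in section 15. The laboratory must confirm that sample handling suits an activity assay, which the documents do not address. An early post-reperfusion blood sample is optional.
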